Among subjects with SCLC treated with rovalpituzumab tesirine 0.3 mg/kg q6w, 96.8% of subjects reported at least 1 adverse event. The most frequently reported adverse events among subjects with SCLC treated with rovalpituzumab tesirine 0.3 mg/kg q6w were decreased appetite (28.0%), photosensitivity reaction (27.7%), oedema peripheral (27.2%), dyspnoea (26.6%), and nausea (25.6%). Important identified risks following treatment with rovalpituzumab tesirine include: pleural effusions (33.9%), pericardial effusions (16.7%), generalized edema (2.7%) and photosensitivity reactions (27.7%). Important potential risks following treatment with rovalpituzumab tesirine include pneumonitis (1%). The following adverse events of special interest have also been identified: cutaneous reactions (48.7%), thrombocytopenia and hemorrhage events (28%), edema (33.8%), hypoalbuminemia (16.2%), hepatotoxicity (19.3%), nephrotoxicity (5.9%), anemia (19.7%), neutropenia (9.2%) and infusion related reaction (0.2%). In addition, preclinical toxicology studies conducted in the rat and the cynomolgus monkey have identified bone marrow, lung, and kidney as potential sources of clinical adverse events (AEs) (AbbVie Investigator Brochure v7). Accordingly, safety assessments will include regular assessments at protocol-specified time points of routine physical examination, laboratory and imaging tests including CT/MRI assessments and echocardiograms, a fluid retention questionnaire, and daily weights (Section 5.3.1.1). The timing and frequency of these assessments are designed so that potential rovalpituzumab tesirine-related toxicities are identified prior to additional drug doses, limiting the risk of toxicity exacerbation. The dose delay/reduction/discontinuation protocol guidelines provide additional level of risk mitigation for subjects enrolled in this study.

It is thus considered that the study has acceptable benefit/risk profile for subjects with ED SCLC and stable disease or better following completion of four cycles of platinum-based standard front line treatment, taking into account short progression-free and overall survival of these subjects.

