11.0 Safety Analysis

11.1 General Considerations

Unless otherwise specified, safety analyses will be performed on the Safety Set. No statistical comparisons will be performed between arms. No p-values and CIs will be provided.

Unless specified, all summaries/analyses involving AEs will only include treatment-emergent adverse events (TEAEs). TEAEs are defined as any adverse event with onset or increase severity after the first dose of study drug (rovalpituzumab tesirine or matching placebo; dexamethasone or matching placebo) and no more than 70 days after the last dose of study drug administration. AEs where the onset date is the same as the study drug start date are assumed to be treatment-emergent, unless the study drug start time and the AE start time are collected and the AE start time is prior to the study drug start time. If an incomplete onset date was collected for an AE, the AE will be assumed to be treatment-emergent unless there is evidence that confirms that the AE was not treatment-emergent (e.g., the AE end date was prior to the date of the first dose of study drug).

Adverse events will be coded and summarized by system organ class and preferred term (and severity) according to the Medical Dictionary for Regulatory Activities (MedDRA) version 21.0 or higher. The table of clinical toxicity grades modified from the National Cancer Institute Common Terminology Criteria for Adverse Events (NCI CTCAE) version 4.0 will be used in the grading of adverse events and laboratory abnormalities that are reported as adverse events.

Summary of continuous safety endpoints (e.g., change from baseline values in laboratory values, vital signs parameters) will include the mean, standard deviation, median and range. In the context of change from baseline analyses, summary of baseline and post-baseline data will also be provided. Categorical safety endpoints (e.g., incidence of AEs or clinically significant ECG values) will be summarized using frequencies and percentages. All the analyses will be carried out by treatment group.

Unscheduled assessment will not be included in the summary of change from baseline, but will be included in producing shift tables and summary of lab abnormalities.

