Cutaneous Reaction	SOC 10040785 Skin and Subcutaneous Tissue Disorders The observed TEAEs under this SOC will be medically adjudicated to maintain a list of PTs that are not medically relevant and that will be excluded from the analysis. Current list of PTs to exclude: 10001760 Alopecia 10002424 Angioedema 10011985 Decubitus Ulcer 10014080 Ecchymosis 10020642 Hyperhidrosis 10051235 Madarosis 10070533 Nail Bed Disorder 10028694 Nail Disorder 10062283 Nail Ridging 10028692 Nail Discolouration 10029410 Night Sweats 10034754 Petechiae 10037087 Pruritus 10052576 Pruritus generalised 10037549 Purpura 10042682 Swelling Face
Edema	PTs: 10030095 Oedema 10030124 Oedema Peripheral 10048961 Localised Oedema 10018092 Generalised Oedema 10042674 Swelling 10016807 Fluid Retention 10016803 Fluid Overload 10024770 Local Swelling 10048959 Peripheral Swelling 10007196 Capillary Leak Syndrome 10015993 Eyelid Oedema 10016029 Face Oedema 10052139 Eye Oedema 10034545 Periorbital Oedema
Hepatotoxicity	SMQs: 20000007 Drug-Related Hepatic Disorders (severe events only; broad) 20000009 Cholestasis and Jaundice of Hepatic Origin (broad) 20000008 Liver Related Investigations, Signs and Symptoms (broad) Exclude PT 10020942 Hypoalbuminaemia from this search since hypoalbuminemia is associated with chronic liver disease and therefore not included in AESI

Time to onset

Time to onset is the Rx Day of the start date of the first occurrence of AESI. If a subject has not experienced an AESI, the subject will be censored on the day of the subject's last assessment (i.e., the day of the subject's last known laboratory assessment, last known vital sign assessment, last known physical exam, last known tumor assessment, or last known follow-up visit, whichever is the latest) or 70 days from the last study drug administered, whichever is earliest; if the subject has not experienced an AESI and had no post-baseline assessment (i.e., none of laboratory assessment, vital sign assessment, physical exam, or tumor assessment), the subject will be censored on the day of the subject's first study drug.

Median onset time will be estimated using a Kaplan-Meier method with corresponding 95% CI for the median for each treatment arm.

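### The only planned AESI onset summary, a Kaplan-Meier median over all treated subjects, will usually be not reached for the rarer AESIs, and for the commoner ones its label can mislead

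*SAP*

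**What the plan says.** SAP 11.3 defines time to onset as the Rx Day on which the first occurrence of the AESI starts. For everyone else, "If a subject has not experienced an AESI, the subject will be censored on the day of the subject's last assessment", "or 70 days from the last study drug administered, whichever is earliest". The output is a per-arm median: "Median onset time will be estimated using a Kaplan-Meier method with corresponding 95% CI for the median for each treatment arm".

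The population follows from SAP 11.1: "Unless otherwise specified, safety analyses will be performed on the Safety Set". That is every subject who received at least one dose, affected or not.

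SAP 11.2 to 11.4 otherwise give counts, percentages and listings. No cumulative incidence at fixed times is planned, and no onset summary restricted to affected subjects.

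Protocol 3.5 gives incidences in SCLC subjects treated at 0.3 mg/kg every 6 weeks. The important identified risks are "pleural effusions (33.9%), pericardial effusions (16.7%), generalized edema (2.7%) and photosensitivity reactions (27.7"%), and pneumonitis is put at 1%. The others include "cutaneous reactions (48.7%), thrombocytopenia and hemorrhage events (28%), edema (33.8%), hypoalbuminemia (16.2"%), hepatotoxicity 19.3%, anemia 19.7%, and "neutropenia (9.2%) and infusion related reaction (0.2"%).

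SAP 11.1 also states, for safety analyses in general: "No p-values and CIs will be provided". SAP 11.3 nonetheless plans a 95% CI.

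**The concern.** A Kaplan-Meier median exists only if the estimated event-free curve falls to 50% or below. Every AESI incidence in Protocol 3.5 is below 50%, several are far below, and observation closes no later than 70 days after the last dose. For many AESIs the planned output may therefore be blank, or may rest on the few subjects still under observation late on.

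Where the median can be estimated, it answers a different question from the one its label suggests. A reader of a safety table is likely to take *median onset time* as the usual day on which the event starts in people who get it. The planned statistic is the day by which half of all treated subjects would have had the event, if death and the end of the window carried no information about risk.

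Timing is of practical interest here. Protocol 3.5 says assessments are timed so that toxicities are found before further doses, and Protocol 6.1.8.1 and 6.1.8.4 note that effusion and edema events may occur up to several months after the last dose. At stake is whether the study report describes timing usefully. No endpoint or decision rule depends on it.

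**Working it through.** The documents give no onset figure to reproduce, so the planned statistic was simulated from their own inputs.

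**Inputs from the documents**
- About 370 subjects per arm (740 at 1:1; SAP 4.3 and 4.4).
- Rova-T median PFS 4.5 months and median OS 13 months (SAP 4.4), taken as exponential. A second set used the placebo assumptions, 3 and 9 months.
- Dosing on days 1, 43, 127, 169 and so on (SAP 4.2, every third cycle omitted), until progression is found at a 6-weekly scan.
- Censoring at last dose + 70 days or death. The last-assessment limit was not modelled separately; it could only shorten follow-up.
- Crude incidences from Protocol 3.5.

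**Assumptions not in the documents.** The onset shape is not stated. Three were used, each calibrated so that the crude incidence inside the window equals the protocol figure: constant hazard; early-weighted hazard (Weibull, shape 0.6); and a model in which only a fraction q of subjects is susceptible, with median onset of 21, 45 or 90 days.

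**Step 1, length of observation.** The simulated Rova-T window has median 113 days (interquartile range 71 to 239).

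**Step 2, is the median reached?** The criterion is S(t) ≤ 0.5 at some observed t. Results for Rova-T assumptions, constant / early-weighted hazard:

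| Crude incidence | Trials reaching the median | KM median when reached (days) | Median onset among affected (days) |
|---|---|---|---|
| 0.2% infusion related reaction | 0% / about 0% | – | – |
| 1% pneumonitis | 2% / 1% | 909 / 854 | 102 / 57 |
| 2.7% generalized edema | 4% / 1% | 949 / 890 | 99 / 50 |
| 9.2% neutropenia | 27% / 10% | 713 / 801 | 94 / 50 |
| 16.2% hypoalbuminemia | 64% / 15% | 583 / 696 | 89 / 46 |
| 19.7% anemia | 81% / 29% | 489 / 630 | 86 / 44 |
| 27.7% photosensitivity | 100% / 71% | 335 / 469 | 78 / 41 |
| 33.9% pleural effusion | 100% / 95% | 259 / 344 | 74 / 39 |
| 48.7% cutaneous reactions | 100% / 100% | 147 / 147 | 62 / 34 |

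A repeat run gave 0-28% at 9.2% or less and 19-69% at 16.7% (pericardial effusion), with about 1 to 6 subjects at risk when the median was reached. Under constant hazard about 24 to 35 remain at risk at 27.7-33.9%, and about 76 at 48.7%.

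**Step 3, susceptible fraction.** The event-free curve levels off at 1 − q, so no population median exists if q < 0.5. Pleural effusion with 45-day onset needs q = 0.42, a plateau of 1 − 0.42 = 0.58, and the median is reached in 1% of trials. Over the three onset medians it is reached in 0-12% of trials at 27.7%, 0-75% at 33.9%, and 81-100% at 48.7%.

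**Step 4, what the number means when reached.** The ratio of KM median to affected-only median is 147/62 = 2.4 to 147/34 = 4.3 at 48.7%, 259/74 = 3.5 to 344/39 = 8.8 at 33.9%, and 335/78 = 4.3 to 469/41 = 11 at 27.7%. This measures the gap between two different quantities; it is not a bias. Under constant hazard the true population median is ln 2 divided by the hazard, and the KM median matches it: 145 against 146 days at 48.7%, 254 against 257 days at 33.9%.

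**Step 5, other arm.** With PFS 3 and OS 9 months and the same incidences the pattern holds: at 48.7%, about 110 days against 26 to 49 among affected subjects.

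**The case against.** The strongest reply is that the Kaplan-Meier median is a valid estimator of a whole-population quantity, and that censoring where observation ends is what the method is for. AEs are collected, and count as treatment-emergent, only to 70 days after the last dose. This stands, and it rules out several stronger readings.

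- **That the KM median is far later than the real onset.** Step 4 does not support this: under constant hazard the KM median matches the true population median. The affected-only median is short partly because only events inside a window of about 113 days can be seen.
- **That an incidence below 50% means the median cannot be reached.** With heavy censoring it can be, and at 48.7% it was in every simulated trial under constant or early-weighted hazard.
- **That AESIs are known to begin in the first cycles.** The documents do not say so; the short onset times come from assumed shapes.
- **That censoring deaths will overstate cumulative risk.** SAP 11.3 plans no cumulative-risk estimate, and SAP 11.2 reports crude percentages.

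Two further points stand in part. The incidences are earlier-programme data. They could be higher here with dosing until progression, and are likely lower on placebo, where the median would be harder still to estimate. SAP 11.3 also does not say whether the analysis is per category or pooled. If pooled, with a crude incidence assumed at 70-90%, the median would be estimable and only about 1.2 to 1.8 times the affected-only figure. SAP Table 3 lists separate categories, so per category is the natural reading, but it should be stated.

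On the CI, one can argue that the specific provision in 11.3 overrides the general one and that an interval for a within-arm median is not a comparison. That explains the intent. The two sentences still conflict as written, because the opening exception in 11.1 attaches only to the sentence on the analysis set.

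**Conclusion.** The point holds as a minor reporting weakness. At the Protocol 3.5 incidences the only planned onset summary will usually be not reached for AESIs at about 10% or less. At about 16-20% it will often be not reached, or will rest on very few subjects. For commoner AESIs it is usually estimable under constant hazard, and less reliably if onset is early-weighted or only a fraction is susceptible. It then describes the whole treated population, with death treated as non-informative censoring, and not the typical onset among affected subjects. The fault in that range is the label and its likely reading.

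The sizes rest on earlier-programme incidences, the design PFS and OS medians, assumed onset shapes, and a per-category analysis. Poor estimability for the rare AESIs does not depend on which shape is chosen; the figures at 16-34% do.

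**What to change.** In SAP 11.3:
- State that time to onset is analysed separately for each AESI category in Table 3.
- Report cumulative incidence by arm at fixed times, for example weeks 6, 12 and 18, with death as a competing event.
- Add the median and range of onset day among affected subjects, labelled as conditional on onset within the observation window.
- Keep the Kaplan-Meier median only where it is reached with adequate numbers at risk, and describe it as the time by which half of all treated subjects would be affected.

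In SAP 11.1, say whether confidence intervals are given for within-arm safety estimates, so that it agrees with 11.3.

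The cost is a few lines of text and a few extra descriptive tables from data already collected. The affected-only median has its own limitation, truncation by follow-up, which is why it should sit beside the cumulative incidence and not replace it.

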11.4 Listing of Adverse Events

The following additional summaries of adverse events will be provided:

- Listing of treatment-emergent serious adverse events
- Listing of treatment-emergent adverse events that lead to discontinuation of study drug
- Listing of treatment-emergent fatal adverse events
- Listing of Grade 3 or higher adverse events
- Listings of SAEs leading to death
- Listings of SAEs leading to treatment discontinuation.

11.5 Analysis of Laboratory, Vital Signs, and ECG Data

Clinical laboratory variables are listed in [Table 4](#).

For laboratory (hematology, chemistry, urinalysis, and coagulation), vital signs, and ECG parameters, changes from baseline are analyzed for each post-baseline visit (as specified

in Section 6.0 Analysis of Conventions) and the final visit. If more than one measurement exists for a subject on a particular day, an arithmetic average will be calculated and considered to be the subject's measurement of that day.

Descriptive statistics will be presented for baseline, each post-baseline, and the final visit (the last valid record) by each treatment arm. Mean change from baseline to each post baseline visit, and to the final visit within each treatment arm will also be presented. The highest and lowest values of each parameter will be identified for each subject, and descriptive statistics for mean change from baseline within each treatment arm will be presented.

Laboratory grade determinations will be categorized according to NCI CTCAE version 4.0 grades, and shifts from baseline grades to maximum and final post-baseline grades will be assessed. The baseline and final grades will be defined respectively as the grade of the last measurement collected prior to or on the first dose of study drug, and as the grade of the last post-baseline measurement collected no more than 70 days after the last dose of study drug. Frequency and percentage of subjects will be presented by treatment arm: 1) baseline grade vs. maximum post-baseline grades, and 2) baseline grade vs. final post-baseline grade. Frequency and percentage of subjects experiencing a shift from baseline grades of 0 to 2 to maximum post-baseline grades of 3 to 4, and from baseline grades of 0 to 2 to final post-baseline grades of 3 to 4 will be presented by treatment arm.

Detailed listings of data for subjects experiencing NCI CTCAE grade 3 to 4 biochemistry and hematology values will be provided. All measurements collected, regardless of the number of days after the last dose of study drug, will be included in these listings. A listing will be provided for out-of-normal range as well as clinically significant abnormal lab values.

Descriptive summary statistics for categorical ECG status data will be presented for baseline and post-baseline visits. Shift tables will also be provided.

Table 4. Clinical Laboratory Tests

Hematology	Clinical Chemistry	Urinalysis (Dipstick)
Hematocrit Hemoglobin Red blood cell (RBC) count White blood cell (WBC) count Neutrophils Bands (if indicated) Lymphocytes Monocytes Basophils (if indicated) Eosinophils (if indicated) Platelet count (estimate not acceptable) Mean corpuscular volume Mean corpuscular hemoglobin concentration RBC distribution width	Blood urea nitrogen (BUN) Serum creatinine Total bilirubin Serum glutamic-pyruvic transaminase (SGPT/ALT) Serum glutamic-oxaloacetic transaminase (SGOT/AST) Alkaline phosphatase Sodium Potassium Calcium Inorganic phosphorus Uric acid Total protein Glucose Albumin Magnesium Chloride Amylase Lipase Lactate dehydrogenase (LDH)	Specific gravity Ketones pH Protein Blood Glucose Urobilinogen Bilirubin Leukocyte esterase
Coagulation		Serum Pregnancy Test
Activated Partial Thromboplastin Time (aPTT) Prothrombin time (PT) International Normalized Ratio (INR)		Beta-Human Chorionic Gonadotropin (β -hCG) (if applicable) Follicle-stimulating hormone (FSH) (if applicable)

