#### **Vital Signs**

Vital signs will be performed per Appendix C, Study Activities. Vital signs include actual weight, sitting blood pressure, heart rate and body temperature. If possible, blood pressure and heart rate measurements should not immediately follow scheduled blood collections.

Actual weight will be collected in the clinic prior to dosing at each cycle and the recorded weight will be utilized for dosing calculations. For weight assessments, the subject should not wear shoes. In the event of a 5% or greater increase in weight within 2 consecutive visits or compared to baseline which ever has the shorter interval, a prompt workup for fluid retention (e.g., edema, effusions, etc.) should be conducted. If weight gain is due to proven or suspected fluid retention related to study drug, and dosing is not prohibited per Section 5.5.4, dose should be calculated based on actual weight before the event of fluid retention.

Vital signs should be collected prior to the infusion.

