#### Fluid Retention Questionnaire (Including Subject Daily Weight)

Throughout the treatment period as outlined in the Appendix C, Study Activities, subjects will be asked about the development of any new or worsening peripheral edema or dyspnea (Appendix I, Fluid Retention Questionnaire). The assessments on Days 8, 15, 29, and 36 may take place by phone, with the site contacting the subject and reviewing the questionnaire.

[figure not shown]
Starting on Day 1 through the EOT visit, subjects will maintain a diary of daily weights (captured on the Fluid Retention Questionnaire). Subjects should be instructed to use a consistent device throughout the study. The site will advise subjects to contact the site in cases where sudden weight gain (5% or greater) is observed for possible assessment in the clinic.

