# 8.2.3 Vital Signs

Vital signs including pulse, blood pressure, temperature, and body weight will be summarized by treatment arm and time point. For each assessment of vital signs, change from baseline will be summarized by treatment arm.

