6.5 Definition of Study Days and Rx Days

Study Day of any observation is defined for post-randomization observations as:

$$\text{Study Day} = \text{Date of observation} - \text{Date of randomization} + 1,$$

and for observations pre-dating randomization as:

$$\text{Study Day} = \text{Date of observation} - \text{Date of randomization}.$$

Thus, the day of randomization is defined as Study Day 1, while the day prior to the randomization is defined as Study Day –1 (there is no Study Day 0).

Study Rx Day of any post-baseline observation is defined as the number of days from the day of the first dose of any study drug (rovalpituzumab tesirine, Dexamethasone, matching placebo) to the date of observation. It is calculated for each post-treatment observation as follows:

$$\text{Study Rx Day} = \text{Date of observation} - \text{Date of first dose of any study drug} + 1$$

Definition of Analysis Windows

During the treatment period, all time points and corresponding time windows are based on Study Rx Days, unless specified otherwise. For longitudinal analyses, especially for the laboratory data (hematology, chemistry, and urinalysis), the time windows specified below describe how data collected at protocol specified visits will be assigned to. If more than one observation is included in a time window, the observation closest to the nominal day should be used. If there are two observations equally distant to the nominal day, the later one will be used in analyses.

Table 1. Visit Window for Laboratory[#], Vital Sign Assessments and Physical Examination

Study Visit (Week) [*]	Nominal Study Rx Day	Time Window (Study Rx Days Range)
Baseline	1	≤ 1
3	22	2 to ≤ 32
6	43	33 to ≤ 53
9	64	54 to ≤ 74
12	85	75 to ≤ 106
18	127	107 to ≤ 137
21	148	138 to ≤ 158
24	169	159 to ≤ 179
27	190	180 to ≤ 200
30	211	201 to ≤ 232
...
...
18•X	7•18•X + 1	7•18•X - 19 to ≤ 7•18•X + 11
18•X + 3	7•(18•X + 3) + 1	7•18•X + 12 to ≤ 7•(18•X + 3) + 11
18•X + 6	7•(18•X + 6) + 1	7•(18•X + 3) + 12 to ≤ 7•(18•X + 6) + 11
18•X + 9	7•(18•X + 9) + 1	7•(18•X + 6) + 12 to ≤ 7•(18•X + 9) + 11
18•X + 12	7•(18•X + 12) + 1	7•(18•X + 9) + 12 to ≤ 7•(18•X + 12) + 22
...

laboratory tests include hematology, serum chemistry and urinalysis.

* Every third cycle (6-week cycle) treatment will be omitted.

Table 2. Visit Window for Coagulations Tests and Patient Reported Outcomes (PRO)

Study Visit (Week)*	Nominal Study Rx Day	Time Window (Study Rx Days Range)
Baseline	1	≤ 1
6	43	2 to ≤ 64
12	85	65 to ≤ 106

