11.6 Analysis of ECOG Performance Status

ECOG performance status will be summarized for each visit by treatment arm. Shifts from baseline to the best and worst post-baseline score will be tabulated.

11.7 Analysis of Vital Signs Using Criteria for Potentially Clinically Significant Vital Sign Values

Vital signs values will be assessed for potential clinical significance through the application of criteria developed by the sponsor as detailed in the table below.

Systolic Blood Pressure	> 150 mmHg and > 20 mmHg higher than baseline < 70 mmHg and a decrease of ≥ 30 mmHg from baseline
Diastolic Blood Pressure	> 100 mmHg and higher than baseline < 50 mmHg and a decrease of ≥ 20 mmHg from baseline
Pulse Rate	> 120 bpm and an increase of ≥ 30 bpm from baseline < 50 bpm and a decrease of ≥ 30 bpm from baseline
Temperature	$\geq 38.9^{\circ}\text{C}$ $\leq 35.6^{\circ}\text{C}$

The number and percentage of subjects with post baseline values meeting Criteria for Potentially Clinically Significant Vital Signs values will be summarized. Except for the temperature, subjects who have a baseline measurement and at least one post-baseline measurement will be included in the summary. A separate listing of all the subjects and values that meeting the criteria will be provided. No comparisons of the rates of subjects met the above criteria between the treatment arms will be performed.

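### SAP 11.7 has no weight-gain criterion and, on its plain reading, SAP 11.1 drops unscheduled clinic weights from the peak-weight summary (minor)

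*SAP*

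**What the plan says.** Protocol 8.2.3 defines what is to be reported: "Vital signs including pulse, blood pressure, temperature, and body weight will be summarized by treatment arm and time point". SAP 11.5 carries this out by visit: "For laboratory (hematology, chemistry, urinalysis, and coagulation), vital signs, and ECG parameters, changes from baseline are analyzed for each post-baseline visit". It then adds a per-subject extreme, "The highest and lowest values of each parameter will be identified for each subject", and reports it as mean change from baseline by arm.

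SAP 11.7 adds outlier counts: "Vital signs values will be assessed for potential clinical significance through the application of criteria developed by the sponsor". Its table has limits for systolic pressure, diastolic pressure, pulse rate and temperature. There is no row for weight.

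SAP 11.1 restricts the data used: "Unscheduled assessment will not be included in the summary of change from baseline". Its only exceptions are shift tables and the summary of laboratory abnormalities, and SAP 11.5 plans shift tables for laboratory grades and ECG, not for vital signs. For windowed analyses, SAP 6.5 says: "If more than one observation is included in a time window, the observation closest to the nominal day should be used".

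The protocol has its own weight threshold. Section 5.3.1.1 (Vital Signs) begins the rule "In the event of a 5% or greater increase in weight within 2 consecutive visits or compared to baseline", adds that the comparison with the shorter interval applies, and requires a prompt workup for fluid retention. If fluid related to study drug is the proven or suspected cause and dosing is allowed, the dose is calculated on the weight before the fluid event. Under Fluid Retention Questionnaire, the site tells subjects to "contact the site in cases where sudden weight gain (5% or greater) is observed for possible assessment in the clinic".

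**The concern.** Fluid retention is a known toxicity of this drug. Protocol 3.5 lists pleural effusion, pericardial effusion and generalized edema as important identified risks, and protocol 6.1.8.4 mentions fatal generalized edema. Amendment 4 added the 5% weight rule, and the SAP is written to Amendment 4. Yet the SAP has no table showing how many subjects per arm had such a gain.

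The second part concerns which weights count. A subject who notices a sudden gain and is weighed at an extra visit produces an unscheduled value. If the SAP 11.1 exclusion reaches the highest-value summary, the weights taken because something was wrong are the ones left out. At stake is the completeness of a descriptive safety comparison in a placebo-controlled trial, where counts by arm are easy to interpret.

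**Working it through.** The plan states no figure to reproduce. The check sets the rules side by side and works one assumed case.

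**1. Coverage of vital signs.** Protocol 8.2.3 names pulse, blood pressure, temperature and body weight. SAP 11.7 covers blood pressure (systolic and diastolic), pulse and temperature. The difference is body weight alone.

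**2. Which weights enter the peak summary.** SAP 11.5 finds each subject's highest value and reports it as change from baseline. SAP 11.1 keeps unscheduled assessments out of change-from-baseline summaries, and neither exception applies to weight. Read together, the highest weight is taken over scheduled visits only. SAP Table 1 places these at Rx Days 22, 43, 64, 85 and 127, so extra clinic weights would fall in intervals of 21 or 42 days.

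**3. Direction within a subject.** The maximum over scheduled weights can never exceed the maximum over all weights. The exclusion therefore lowers the reported peak or leaves it unchanged. If the peak falls at a scheduled visit, the loss is zero.

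**4. Assumed case.** Baseline 70 kg; scheduled weights 70.7 kg and then 71.0 kg; one unscheduled weight of 73.5 kg between them.

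| Weights used | Highest | Change | Percent of baseline |
|---|---|---|---|
| Scheduled only | 71.0 kg | 71.0 - 70 = 1.0 kg | 1.0/70 = 1.4% |
| Including unscheduled | 73.5 kg | 73.5 - 70 = 3.5 kg | 3.5/70 = 5.0% |

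This subject is 5% above baseline at the peak, and on the plain reading no planned weight summary shows it.

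**5. The definition matters.** Measured from the preceding visit, the same gain is (73.5 - 70.7)/70.7 = 2.8/70.7 = 4.0%. If the shorter-interval qualifier is applied literally and the extra weighing counts as a visit, the subject does not meet the protocol trigger, although weight is 5.0% above baseline. A count of 5% or more above baseline and a count of protocol triggers are therefore different quantities.

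**6. The kilogram summary cannot supply the count.** A highest gain of 4 kg is 4/50 = 8.0% for a 50 kg subject and 4/100 = 4.0% for a 100 kg subject. A mean change in kilograms does not show how many passed 5%.

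**7. What cannot be computed.** The number of unscheduled weights, how long gains last, and how either differs by arm are not in the documents. The share of gains falling between scheduled visits could be calculated for an assumed duration, but it would describe gaps in the visit schedule, not error in the analysis.

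**The case against.** The strongest reply is that SAP 11.5 does not limit the highest value to scheduled visits. The closest-to-nominal-day rule in SAP 6.5 is for longitudinal analyses, and the SAP 11.1 exclusion may be meant only for by-visit tables. Read that way, peak weight is fully captured. This stands as a possible reading. It is less natural, because the extreme is itself reported as change from baseline, but it means the SAP is unclear and an omission is not proved.

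A reader might infer that only an unscheduled clinic weight could reveal a gain between visits. The protocol does not support that: subjects record weight daily through end of treatment, and sites review the questionnaire about weekly, including in the non-treatment cycle. The gains are seen in conduct. What remains is that the SAP plans no summary of the diary.

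A reader might also infer that pericardial effusion is poorly reported because the scheduled echocardiograms have no table by arm. That goes too far. In protocol Appendix H even a small asymptomatic pericardial effusion is Grade 2. Changes from baseline go on the adverse-event form (5.3.1.1), drug-related effusions must resolve before dosing (5.5.4.1), and Table 5 makes dose reduction mandatory at Grade 2. Such findings already have a route to the adverse-event, special-interest and dose-modification tables. An echocardiogram table would largely repeat them, and the documents do not show whether the results are in the database.

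Finally, protocol 8.2 asks only that weight be summarized, and SAP 11.5 does that. This is not a departure from the protocol. The Edema search in SAP 11.3, which includes fluid retention and fluid overload, will catch many events. It has no weight-gain term, and protocol 6.1.1.1 makes a vital-sign change an adverse event only under certain conditions, so it does not replace a weight count.

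**Conclusion.** The point holds as a minor one. SAP 11.7 leaves out the one vital sign for which the protocol has a specific fluid-retention threshold. On the plain reading of SAP 11.1, clinic weights taken because of a sudden gain can also drop out of the peak-change summary, and any such error lowers the reported peak. The 1.4% against 5.0% contrast rests on assumed weights and shows only what can happen.

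The documents give neither the size of the understatement nor its direction between arms. It is tempting to conclude that the drug's excess of fluid retention will be understated. That would need unscheduled weights to be more frequent or larger in one arm, which nothing here shows. The primary endpoints, alpha and the futility rule are not affected.

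**What to change.** Make two descriptive changes, by arm in the Safety Set, with no p-values, as SAP 11.1 already provides.

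1. In SAP 11.1 or 11.5, state that unscheduled clinic weights are included in the highest-value weight summary.
2. In SAP 11.7, add a row for weight gain of 5% or more, n (%), counting unscheduled clinic weights. Either use the full protocol 5.3.1.1 rule, including the shorter-interval qualifier, or label the row as a simpler count of 5% or more above baseline that is not the protocol trigger. Footnote that weight gain is not specific to fluid and that the count depends on time on treatment.

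The cost is one sentence and one table row on data already collected.

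Optionally, if echocardiogram results are in the database, add a count by arm of new pericardial effusion on scheduled echocardiograms as a cross-check on the special-interest event rate. The finding does not depend on it.
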